7.4.2 Routine Reporting

- All other adverse events- such as those that are expected, or are unlikely or definitely not related to the study participation- are to be reported annually as part of regular data submission. This report should also be forwarded to

the DSMC Coordinator. A list of all toxicities will be included in the IND annual report.

7.5 Stopping Rules (Monitoring rules for safety)

Although we expect that regorafenib be well tolerated, the guidelines listed below will be used to raise a flag if the number of patients who experience unacceptable toxicity is large enough to strongly suggest that the true probability of unacceptable toxicity is 33% or higher.

Unacceptable toxicity will be defined as

- Any Grade 3 non-hematologic toxicity not reversible to Grade 1 or less within 96 hours with the exception of Grade 3 diarrhea or
- Any Grade 4 non-hematologic toxicity or
- Any Grade 4 hematologic toxicity not resolving to Grade 1 or less within 5 days, despite supportive care or
- Grade 4 neutropenia associated with fever or
- Grade 4 thrombocytopenia.

An unacceptable toxicity, regardless of attribution, observed during any course, will be used in the decision to suspend accrual. Two cohorts will be monitored separately.

To be evaluable for excessive toxicity a patient must complete a minimum of 2 courses of treatment or have experienced unacceptable toxicity. Patients who do not complete 2 courses and who do not experience any unacceptable toxicity will not be used in the decision to continue or suspend accrual to the trials, for reasons for excessive toxicity. Every time unacceptable toxicity is observed, the number of patients (X) who have experienced unacceptable toxicity will be compared to the number of patients (N) who are evaluable for excessive toxicity. If the number of patients, N, is greater than N_x , the number given in column 2 of the Table XX, below, then accrual will not be suspended. If N is less than or equal to N_x , then accrual will be suspended for review of the data.

Table XX: Criteria for continuing accrual

X: # pts who experienced a DLT in a cohort	3	4	5	6	≥ 7
N_x : Suspend trial of # evaluable pts. (N) is $\leq N_x$ in a cohort	≤ 5	≤ 10	≤ 15	≤ 20	suspend

Using this rule with 24 patients, the probability of correctly suspending this regimen for review toxicities is 0.79 if the true chance of unacceptable toxicity is 33%. The probability of falsely suspending this regimen for review toxicities is 0.030, if the true chance of unacceptable toxicity is 10%. Estimations of the probabilities of suspending this regimen are based on 10,000 simulations.

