7.2.2 Severity of Adverse Events

All adverse events will be graded according to the NCI Common Terminology Criteria for Adverse Events (CTCAE) version 4.0. The CTCAE v4 is available at <http://ctep.cancer.gov/reporting/ctc.html>

If no CTCAE grading is available, the severity of an AE is graded as follows:

Mild (grade 1): the event causes discomfort without disruption of normal daily activities.

Moderate (grade 2): the event causes discomfort that affects normal daily activities.

Severe (grade 3): the event makes the patient unable to perform normal daily activities or significantly affects his/her clinical status.

Life-threatening (grade 4): the patient was at risk of death at the time of the event.

Fatal (grade 5): the event caused death.

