7.4 Reporting Requirements for Adverse Events

7.4.1 Expedited Reporting

- The Principal Investigator must be notified within 24 hours of learning of any serious adverse events, regardless of attribution, occurring during the study or within 30 days of the last administration of the study drug.
 - Study Chair/USC PI: [name] ([contact])
 - Multi-site Coord./DSMC Coord.: [name] ([contact])
- SAE occurring after consent but before first dose will not require reporting.
- **The Investigator may report serious adverse drug reactions (SADRs) using either:**

A MedWatch form available at <http://www.fda.gov/medwatch/>

All reports shall be sent electronically to:

Electronic Mailbox: [contact]

[contact]

Address: Global Pharmacovigilance - USA
Mail only: Bayer HealthCare Pharmaceuticals Inc.
[name]
[name]

Address: [name]
FDX or UPS only

Reports for all Bayer products can also be phoned in via our Clinical Communications Dept:

[contact]

The investigator must report to Bayer any pregnancy occurring in a study subject, or in his partner, during the subject's participation in this study. The report should be submitted within the same timelines as an SAE, although a pregnancy per se is not considered an SAE.

For a study subject, the outcome of the pregnancy should be followed up carefully, and any abnormal outcome of the mother or the child should be reported.

For the pregnancy of a study subject's partner, all efforts should be made to obtain similar information on course and outcome, subject to the partner's consent.

Progressive disease

If progressive disease leads to signs and symptoms that meet the criteria for an SAE (i.e., hospitalization, disability, death, or important medical event), the signs and symptoms should be reported as an SAE to Bayer and not the underlying progressive disease.

Death

If any subject dies during the trial or within 30 days of the end-of-treatment visit, the investigator will inform Bayer and record the cause of death in detail (within 24 hours).

All non-USC sites are required to notify the study chair, [name] and the multi-site coordinator of all SAE submissions. Investigators should also report events to their IRB as required.

SAE notification to the FDA:

- USC: study team to work with CISO QA to submit to the FDA using MedWatch 3500A form in accordance within the FDA required timelines

-

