Tumor response rate will be calculated as a proportion of patients who have either a complete or partial response among all patients in the primary data analysis set. The 95% confidence intervals will be given.

OS will be analyzed in the same way as PFS.

Toxicity profile will be summarized by attribution: regorafenib-related and all reported, course: cycle 1 and all cycles, type, and grade: grade 1-2, 3-4, and 5.

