10.4 Reporting and Exclusions

10.4.1 Evaluation of toxicity. All toxicities experienced by patients who receive

any treatment of the study drug(s) will be reported.

- 10.4.2 Evaluation of response. All patients included in the study must be assessed for response to treatment, even if there are major protocol treatment deviations or if they are ineligible. Each patient will be assigned one of the following categories: 1) complete response, 2) partial response, 3) stable disease, 4) progressive disease, 5) early death from malignant disease, 6) early death from toxicity, 7) early death because of other cause, or 9) unknown (not assessable, insufficient data).

All of the patients who met the eligibility criteria (with the possible exception of those who never received any study drug) should be included in the main analysis of the response rate. Patients in response categories 4-9 should be considered to have a treatment failure. Thus, an incorrect treatment schedule or drug administration does not result in exclusion from the analysis of the response rate.

The primary analysis will be based on all eligible patients and who received any amount of study drug.

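### The section 7.5 toxicity rule stops at Grade 4, so a fatal toxicity with no earlier listed event is never counted as an event

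*Combined protocol and SAP*

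**What the plan says.** Section 7.5 monitors each cohort separately. Its definition of unacceptable toxicity has five items: certain Grade 3 non-hematologic toxicities that do not reverse in time; "Any Grade 4 non-hematologic toxicity or" (the second item); Grade 4 hematologic toxicity that does not resolve in time; Grade 4 neutropenia with fever; and Grade 4 thrombocytopenia. No item names Grade 5 or death.

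The scope is wide: "An unacceptable toxicity, regardless of attribution, observed during any course, will be used in the decision to suspend accrual". Membership of N is set by: "To be evaluable for excessive toxicity a patient must complete a minimum of 2 courses of treatment or have experienced unacceptable toxicity". Everyone else is left out: "Patients who do not complete 2 courses and who do not experience any unacceptable toxicity will not be used in the decision". X is compared with N only when an unacceptable toxicity is observed. Table XX suspends accrual at X=3 with N≤5, X=4 with N≤10, X=5 with N≤15, X=6 with N≤20, or X≥7. With 24 patients, the stated probability of suspension is 0.79 at a true rate of 33% and 0.030 at 10%.

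Other sections treat a fatal toxicity as a category of its own:

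- Section 10.3 tabulates toxicity by "grade: grade 1-2, 3-4, and 5".
- Section 10.4.2 has the response categories "5) early death from malignant disease, 6) early death from toxicity, 7) early death because of other cause".
- Section 7.2.2, in the scale used where CTCAE gives no grading, has "Fatal (grade 5): the event caused death".

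**The concern.** The list in section 7.5 is closed, and the protocol does not fold Grade 5 into Grade 4 elsewhere. Taken literally, a patient whose only qualifying event is a fatal toxicity does not add to X, and the death does not prompt the comparison of X with N. What happens to N depends on timing:

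- **Before two completed courses:** the patient is in neither X nor N.
- **After two completed courses:** the patient is already in N and stays there as a non-event, which makes suspension slightly less likely.

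Table XX is the plan's only numerical toxicity rule, and it can pass over the most severe outcome. At stake is a pre-specified review of accumulated toxicity that comes later than it should, or is not triggered. Review of the single death would still take place by other routes.

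**Working it through.** **Inputs.** The Table XX limits, 24 patients per cohort and the rates of 33% and 10% are from section 7.5. The documents give no rate for fatal toxicity without an earlier listed event (called fatal-only below), so every value of that rate is an assumption.

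**Method.** Exact recursion over 24 patients in accrual order, tracking (X, N). Each patient is one of:

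- a counted event: X and N both rise by 1, and the limits are checked;
- a non-event: N rises by 1;
- dropped: neither changes.

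The suspension probability is the total probability of all paths that reach a limit.

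**Step 1: the plan's own figures.** With every toxicity counted, the result is 0.7937 at 33% (stated 0.79) and 0.0293 at 10% (stated 0.030). Both reproduce.

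**Step 2: exactly one fatal-only patient.** Place that patient at each of positions 1 to 24 in turn and average. The other 23 have listed events at rate p.

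| p | Death counted | As written, early (dropped) | As written, late (non-event) |
|---|---|---|---|
| 0.33 | 0.8718 | 0.7710 | 0.7552 |
| 0.10 | 0.0690 | 0.0285 | 0.0248 |

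At 33% the loss is 0.8718 − 0.7710 = 0.101 (early) or 0.8718 − 0.7552 = 0.117 (late). This step assumes no fatal-only rate, but it is conditional on one such death having occurred.

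**Step 3: unconditional loss at a total rate of 33%.** Let f be the fatal-only share. Early: event 0.33 − f, dropped f, non-event 0.67. Late: event 0.33 − f, non-event 0.67 + f. If all are counted, the result is 0.7937.

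| f (assumed) | Expected such deaths, 24f | Chance of at least one, 1 − (1 − f)^24 | Early | Late |
|---|---|---|---|---|
| 0.005 | 0.12 | 0.11 | 0.7814 | 0.7794 |
| 0.01 | 0.24 | 0.21 | 0.7687 | 0.7644 |
| 0.02 | 0.48 | 0.38 | 0.7422 | 0.7328 |

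The loss is 1.2 to 1.4 percentage points at f = 0.005, 2.5 to 2.9 at 0.01, and 5.2 to 6.1 at 0.02.

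**Step 4: a small-number example.** The first five patients include two with listed events, one fatal-only death and two non-events.

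- Death counted: X=3, N=5. Accrual is suspended.
- As written, early death: X=2, N=4. A listed event in the next patient gives X=3, N=5 and suspension, one event later.
- As written, late death: X=2, N=5. A listed event in the next patient gives X=3, N=6 (continue). Another in the patient after gives X=4, N=7 (suspend), two events later.

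**Step 5: what counting deaths costs.** Take 10% listed toxicity plus an assumed 0.005, 0.01 or 0.02 fatal-only. Counted, the suspension probability is 0.0349, 0.0412 or 0.0562. As written it is 0.0297, 0.0301 or 0.0311 (early) and 0.0293 (late).

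If progression deaths with no listed event were counted too, at an assumed rate g, the total rate is 0.10 + 0.01 + g. For g = 0.02, 0.05 or 0.10 the suspension probability is 0.0743, 0.1486 or 0.3303.

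**The case against.** The strongest reply is that nobody would apply the rule this way. A toxicity that kills will usually have been Grade 4, or an unresolved Grade 3, on the way; the list is probably shorthand; and section 7.5 presents itself as a flag for review. The grade groupings in section 10.3 and the response categories in 10.4.2 serve other purposes, so the point is an omission and not a contradiction.

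Deaths are also seen elsewhere. Under section 7.4.1 the principal investigator "must be notified within 24 hours of learning of any serious adverse events, regardless of attribution". The same section requires notice of any death to the drug supplier, and notice to the DSMC of events reportable to the IRB. Section 11.6.3 gives the DSMC real-time monitoring. Under sections 6.1.10 and 10.2, a death within 6 months counts against the drug in the stage I efficacy decision.

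On size, step 2 adds one death to 33% listed toxicity in the other 23 patients: 1 + 23 × 0.33 = 8.59 expected events, or 35.8% of 24, above the design point. The unconditional losses in step 3 are small at low fatal-only rates, and the example in step 4 sits on a boundary.

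Most of this stands. It makes the gap narrow and the likely intent benign. It does not close the gap: the list is closed, one sentence expressly removes early patients without a listed event, and none of the other routes puts a death into X or N.

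**Conclusion.** The point holds on the text and should be fixed. The arithmetic in section 7.5 is right, and the primary efficacy analysis is unaffected; the fault is in which events are counted.

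One uncounted fatal-only death lowers the probability of suspension by about 10 to 12 percentage points when listed toxicity runs at 33%. Averaged over whether such a death occurs, the loss is about 1 to 6 points for assumed fatal-only shares of 0.5 to 2 points. Larger losses need higher assumed rates.

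The conclusion rests on a literal reading and on a fatal toxicity with no earlier listed event. The figures also assume that patients become evaluable in accrual order and that fatal-only deaths fall all before, or all after, two completed courses.

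**What to change.** Amend the definition and the evaluability sentence in section 7.5 so that any Grade 5 toxicity counts in X and makes the patient evaluable in N, whatever the number of courses completed. This brings section 7.5 into line with sections 10.3 and 10.4.2.

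In the same place, state whether deaths from disease progression count. The rule applies whatever the attribution, so the text must settle this; the categories in section 10.4.2 already separate malignant-disease deaths from toxicity deaths.

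The cost is one or two sentences and slightly more pauses for review: at 10% listed toxicity and the assumed fatal-only rates, 0.035 to 0.056 against 0.029 to 0.031 as written. Counting progression deaths as well would cost much more, 0.074 to 0.330 under the rates assumed in step 5, so that choice should be explicit. Table XX and the sample size need no change. The 0.79 and 0.030 remain valid because they depend only on the total rate of counted events.

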8.0 DRUG INFORMATION

8.1 Regorafenib

- Other names for the drug(s): Stivarga
- Classification - type of agent: Tyrosine Kinase Inhibitor

- Mode of action: Stivarga (regorafenib) is a potent oral multi-kinase inhibitor with a kinase inhibition profile targeting angiogenic, stromal and oncogenic receptor tyrosine kinases (TK). This distinct anti-angiogenic profile includes inhibition of both VEGFR2 and TIE2 TK.
- Storage and stability: Store Stivarga at 25°C (77°F); excursions are permitted from 15 to 30°C (59 to 86°F) [See USP Controlled Room Temperature]. Store tablets in the original bottle and do not remove the desiccant. Keep the bottle tightly closed after first opening.

Discard any unused tablets 7 weeks after opening the bottle. Dispose of unused tablets in accordance with local requirements.

- Protocol dose: 160 mg qd will be administered for 3 weeks on /1 week off. One cycle is 28 days.
- Preparation: None
- Route of administration for this study: P.O.
- Incompatibilities: See 4.3
- Availability: Provided by sponsor free of charge.
- Side effects: asthenia/fatigue, decreased appetite and food intake, hand-foot skin reaction (palmar-plantar erythrodysesthesia), diarrhea, mucositis, weight loss, infection, hypertension, dysphonia, gastrointestinal and abdominal pain, rash, fever and nausea. See the package insert for a comprehensive list of adverse events.

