Title	Phase II Study of Single Agent Regorafenib in Patients with Advanced/Metastatic Neuroendocrine Tumors
Short Title	Phase II Study of Regorafenib in Advanced/Metastatic Neuroendocrine Tumors
Protocol Number	0S-14-3
Phase	II
Methodology	Open label
Study Duration	Estimate one patient per month accrual. If both cohorts accrue past the interim the study will take 4 years to complete accrual.
Study Center(s)	2
Objectives	
 1. To assess PFS in advanced/metastatic in patients with carcinoid or pancreatic islet cell tumors 2. To assess OS, RR in advanced/metastatic poor prognosis in patients with carcinoid or pancreatic islet cell tumors 3. To assess toxicity of patients treated with regorafenib 4. To explore markers of angiogenesis as they relate to outcome in carcinoid and pancreatic islet cell tumors.
Number of Subjects	Cohort A (Carcinoid Tumors): 11+13=24 Cohort B (Pancreatic Islet Cell Tumors): 11+13=24

Diagnosis and Inclusion Criteria
 
Main
	
Advanced metastatic, progressing carcinoid or pancreatic islet cell cancers
 
*Patients may have received one line of prior therapy with octreotide, locoregional therapy. Continuation of concurrent octreotide is allowed.
 
*No prior targeted tx or anti-angiogenic therapy.
 
*Patients will be maintained on octreotide (sandostatin) for the duration of their treatment.
 
*SWOG PS 0-1

Study Product(s), Dose, Route, Regimen
	
Regorafenib 80 mg QD Week 1/120 mg QD Week 2/160 mg QD Week 3 then 1 week off followed by Cycle 2+ 160 mg QD D1-21, of a 28 day cycle.

Duration of administration
	
Patients may remain on study until the development of disease, development of intolerable toxicity, or any of the criteria for removal of the study as set forth in the protocol.

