The efficacy and safety of regorafenib were examined in the Phase III GRID trial in patients with gastrointestinal stromal tumors (GISTs) who had exhausted all other treatment options. The study involved 199 patients with metastatic and/or unresectable GIST that had become resistant to imatinib and sunitinib. Patients were randomized 2:1 to regorafenib (160 mg orally once daily on a 3 weeks on/1 week off cycle) or placebo, plus best supportive care.

The results showed that treatment with regorafenib led to a statistically significant 3.9-month improvement in progression-free survival (PFS), compared with placebo (4.8 months vs. 0.9 months; hazard ratio [HR] = 0.27; $p < .0001$). Overall survival was statistically similar between groups as expected due to a trial design that allowed crossover to regorafenib for disease progression (85% for placebo and 31% regorafenib randomized patients). The median survival period without tumor growth among patients on regorafenib was 4.8 months while for the control group on placebo it was less than a month. The overall disease control rate combining partial responses with durable stable disease for at least 12 weeks was 53% with regorafenib compared with 9% in the control group. The most common grade ≥ 3 adverse events associated with regorafenib were hand-foot skin reaction (56.1%), hypertension (48.5%), and diarrhea (40.9%). The efficacy and safety of the GRID study data supported FDA approval February 2013.

Recently data from a randomized Phase II study of regorafenib in refractory metastatic colorectal cancer was presented at ASCO GI 2018 by Bekaii-Saab et al. This study randomized patients to Arm A: 80 mg regorafenib per day, with weekly dose escalation of 40 mg, up to a dose of 160 mg per day if no significant drug-related toxicities were observed or Arm B: 160 mg regorafenib per day. Arm A, the dose escalation arm had patients staying on regorafenib longer (43% initiating the 3rd cycle versus 25%, $p = .028$) and had longer overall survival, (9.0 months vs. 5.9 months, $p = .094$). Progression free survival was not statistically significantly longer for Arm A (2.5 months versus 2.0 months, $p = .553$), but rates of overall grade 3/4 toxicity did favor Arm A (% palmar-plantar erythrodysesthesia syndrome 15 versus 16, hypertension 7 versus 15 and fatigue 13 versus 18).

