4.1 TREATMENT PLAN

4.1 Treatment Dosage and Administration

Regorafenib 80 mg QD Week 1/120 mg QD Week 2/160 mg QD Week 3 then 1 week off followed by Cycle 2+ 160 mg QD D1-21, of a 28 day cycle.

Regorafenib tablets should be taken in the morning with approximately 8 fluid ounces (240 mL) of water after a low-fat (<30% fat) breakfast. Some examples of low fat breakfasts are:

- Two slices of white toast with 1 tablespoon of low-fat margarine and 1 tablespoon of jelly and 8 ounces (240 mL) of skim milk (approximately 319 calories and 8.2 g of fat).
- One cup of cereal (i.e. Special K), 8 ounces (240 mL) of skim milk, one piece of toast with jam (no butter or marmalade), apple juice, and one cup of coffee or tea (2 g fat, 17 g

protein, 93 g of carbohydrate, 520 calories.

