4.2.1.1 Dose Levels and Reductions

Study medication will be administered on a 3 weeks on/1week off schedule [3 weeks out of every 4]. A new cycle of therapy can start when all toxicities, (except hand-foot syndrome, alopecia, non-refractory nausea/vomiting, non-refractory hypersensitivity and nonclinical and asymptomatic laboratory abnormalities) have resolved to Grade 2 or less. Hand-foot syndrome must have resolved to Grade 0-1.

Doses will be delayed or reduced for clinically significant hematologic and non-hematologic toxicities that are related to protocol therapy according to the guidelines shown in the Dose Delays/Dose Modifications table that follows. Dose modifications will follow predefined dose levels. Dose adjustments for hematologic toxicity are based on the blood counts obtained in preparation for the day of treatment.

Strictly follow the modification in the following tables for the first **two** cycles until individual treatment tolerance can be ascertained. Thereafter, these modifications should be regarded as guidelines to produce mild-to-moderate, but not debilitating, side effects. If multiple adverse events are seen, administer dose based on greatest reduction required for any single adverse event observed. Reductions or increases apply to treatment given in the preceding cycle and are based on adverse events observed since the prior dose.

Dose Level			If no SDRT	If + SDRT**
Dose level 0*	80 mg po qd	Two 40-mg tablets of regorafenib	Proceed to next dose level	
Dose level 1	120 mg po qd	Three 40-mg tablets of regorafenib	Proceed to next dose level	Decrease to 80 mg
Dose level 2	160 mg po qd	Four 40-mg tablets of regorafenib		Decrease to 120 mg
* Starting Dose				
** SDRT= Significant Drug Related Toxicities				

If a subject experience more than one toxicity, dose reduction should be according to the toxicity with the highest grade

In the case of two or more toxicities of the same grade, the investigator may dose reduce according to that deemed most causally related to study treatment

The following tables outline dose adjustments for toxicities related to study drug except hand-foot skin reaction, hypertension and liver function test abnormalities.

NCI-CTCAE v4.0 ^a	Dose Interruption	Dose Modification ^b	Dose for Subsequent Cycles
Grade 0-2	Treat on time	No change	No change

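### Section 8.1 gives the protocol dose as a flat 160 mg and omits the Cycle 1 step-up, so read literally it doubles the Week 1 dose set elsewhere in the protocol.

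*Combined protocol and SAP*

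**What the plan says.** Four places in the current protocol bear on the Cycle 1 dose.

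- **Section 8.1 (drug information):** "Protocol dose: 160 mg qd will be administered for 3 weeks on /1 week off", with a 28-day cycle. Nothing limits this to Cycle 2 onward, and there is no reference to the treatment plan. Another bullet in the same list does refer the reader elsewhere: "Incompatibilities: See 4.3".
- **Study Summary, dose and regimen row:** "80 mg QD Week 1/120 mg QD Week 2/160 mg QD Week 3 then 1 week off followed by Cycle 2+ 160 mg QD", on Days 1-21 of a 28-day cycle.
- **Section 4.1 (treatment plan):** "Regorafenib 80 mg QD Week 1/120 mg QD Week 2/160 mg QD Week 3 then 1 week off", followed by the same 160 mg regimen from Cycle 2.
- **Section 4.2.1.1, dose-level table:** level 0 is 80 mg (two 40-mg tablets) and its asterisk is explained as "Starting Dose". Levels 1 and 2 are 120 mg and 160 mg, reached by moving up when there has been no significant drug-related toxicity.

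**The concern.** Section 8.1 states what looks like a complete regimen under the label of the protocol dose, and that regimen is wrong for the first 14 days. A reader who works from it would start a patient at 160 mg. The condition in the dose-level table that governs each increase would then never apply, because there would be no increase to govern.

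The section is a plausible place to look up a dose. Section 8.1.1, directly below, covers the study pharmacist's record of doses dispensed at each site, and the Study Summary lists two centers. Section 11.7 requires the study to be run as the approved protocol describes, and Section 11.7.2 counts any variance as a deviation. A site that follows 8.1 for Days 1-14 therefore departs from 4.1, and no rule in the protocol says which section prevails.

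The step-up has a tolerability rationale in the protocol itself. Section 1.2.2 summarizes a randomized phase II study in refractory colorectal cancer that compared weekly escalation from 80 mg with a 160 mg start. Grade 3/4 rates in percent, escalation arm first, were "hypertension 7 versus 15 and fatigue 13 versus 18", and 15 against 16 for hand-foot toxicity. More patients began a third cycle with escalation (43% against 25%, p = .028). The tumor type differs and no p-values are given for the toxicity rates, so these figures indicate direction only.

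**Working it through.** Section 8.1 gives a dose, not a calculated quantity, so there is no statistical figure to reproduce. The check sets the two planned schedules side by side.

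**Inputs.** Section 4.1 and the Study Summary: 80, 120 and 160 mg/day in Weeks 1, 2 and 3 of Cycle 1, then a week off. Section 8.1: 160 mg/day in each of the three weeks on treatment. Section 4.2.1.1: tablet strength 40 mg.

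**Formulas.** Weekly ratio = dose under 8.1 ÷ dose under 4.1. Period total = sum over weeks of 7 × daily dose. Tablets = total ÷ 40.

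| Cycle 1 | Section 4.1 | Section 8.1, literal | Ratio |
|---|---|---|---|
| Week 1, mg/day | 80 | 160 | 160/80 = 2.00 |
| Week 2, mg/day | 120 | 160 | 160/120 = 1.33 |
| Week 3, mg/day | 160 | 160 | 160/160 = 1.00 |
| Days 1-14, mg | 7 × 80 + 7 × 120 = 1,400 | 14 × 160 = 2,240 | 2,240/1,400 = 1.60 |
| Cycle total, mg | 7 × (80 + 120 + 160) = 2,520 | 21 × 160 = 3,360 | 3,360/2,520 = 1.33 |
| Cycle total, tablets | 2,520/40 = 63 | 3,360/40 = 84 | 84/63 = 1.33 |

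The excess is 3,360 − 2,520 = 840 mg, or 21 tablets. All of it falls in Days 1-14, since 2,240 − 1,400 = 840 mg. In Week 3 of Cycle 1, and in the planned dose from Cycle 2 onward, the difference is 0 mg.

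These are planned totals for a patient with no dose-modifying toxicity. A patient held at a lower level under Section 4.2 would receive less than 2,520 mg.

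**The case against.** The strongest reply is that the protocol largely resolves the conflict. Section 8.1 is a reference list covering storage, route and side effects. Section 4.1 is the treatment plan, and the synopsis and dose-level table support it. The 160 mg schedule is also the right planned dose for every cycle after the first, so the bullet is incomplete for 14 days only. That is a fair reading of intent, but it leaves a wrong starting dose in operative text.

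The clinical risk is also bounded:

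- A 160 mg start was the schedule in both phase III trials described in Section 1.2.2, and Table 3 gives 160 mg as the maximum daily dose.
- Toxicity monitoring continues whichever dose is given. Section 5.2.2 requires blood pressure and liver tests on Days 8, 15 and 22 of Cycles 1 and 2, and the dose-modification tables must be followed strictly for the first two cycles. Only the condition on stepping up is lost.
- Under Section 11.6.1 investigators must ensure treatment per protocol, and the Study Coordinator reviews treatment orders with them. Nothing shows that orders or dispensing are built from 8.1.

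All of this stands, and it limits severity without removing the contradiction.

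One further point is correct. Section 4.1 and the synopsis give the escalation as a fixed calendar, while the table makes it conditional on toxicity. They agree on the starting dose and the levels, but only the table states the condition. The corrected bullet should therefore refer to Section 4.2 as well as to 4.1.

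**Conclusion.** The inconsistency is real and should be fixed. The Study Summary, Section 4.1 and the dose-level table all start at 80 mg; Section 8.1 alone does not. Followed literally, 8.1 doubles the Week 1 dose, raises Week 2 by a third, and adds 840 mg over Days 1-14 (60% above plan for those days, 33% above plan for the cycle). This assumes full planned dosing with no toxicity-driven change.

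The consequence is a possible dosing error in the first two weeks, which order review makes less likely but does not rule out. It does not affect sample size, decision rules or error rates, and no effect on the primary endpoint is claimed.

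**What to change.** Keep Section 4.1 as the governing text and replace the dose bullet in Section 8.1 with wording such as:

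> Protocol dose (see Section 4.1): in Cycle 1, 80 mg once daily in Week 1, 120 mg in Week 2 and 160 mg in Week 3, with Week 4 off; from Cycle 2, 160 mg once daily on Days 1-21 of each 28-day cycle. All doses are subject to Section 4.2.

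The reference to Section 4.2 carries over the toxicity condition on each step up. The starting dose and dose levels in the synopsis, Section 4.1 and the dose-level table already agree, so they need no correction on this point. The cost is the wording of one bullet, with no change to design, procedures or statistics.
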